7.6.7 Subgroup Analysis

- 1) For the primary endpoint (DBPC Cycle at Week 6), the following baseline subgroups will be assessed for the mITT population:
 - Aetiology of NDO (SCI or MS)
 - Prior intradetrusor BTX-A usage (BTX-A bladder naïve or BTX-A bladder non-naïve)
 - Age groups (≥ 18 to ≤ 40 , >40 to ≤ 65 , > 65 years)
 - Sex (Male or Female)
 - Concomitant use of anticholinergics and/or beta-3 agonists (Yes or No)
- 2) For the secondary efficacy endpoints included in the hierarchical analysis (DBPC Cycle at Week 6), the following baseline subgroup will be assessed for the mITT population:
 - Aetiology of NDO (SCI or MS)

For 1) and 2) descriptive statistics and statistical analysis will be performed for each subgroup as detailed in section [7.6.3](#) and 7.6.5, with subgroup*treat interaction included in the analysis model. The subgroup analysis will be omitted if the subcategories have fewer than 30 subjects counts.

For 1), the treatment differences and 95% CI will be presented for each subgroup (e.g. Aetiology of NDO: SCI and MS) on a forest plot.

7.7 Safety

All safety data will be included in the subject data listings. Summary tables will be based upon the safety population.

7.7.1 Adverse Events

All AEs will be coded by Sponsor using MedDRA v21.0 (March 2018); (the latest version if updated during the study), and will be classified by MedDRA preferred term and system organ class.

A TEAE is defined as any AE with start date/and time at or after the date/and time of the first dose of IMP, or any AE with start date/and time prior to the date/and time of the first dose of IMP whose intensity worsens at or after the date/time of the first dose of IMP. The Pre-treatment AE is defined as any AE with start date/and time prior to the first dose of IMP administration in DBPC Cycle, and after the date of informed consent.

All TEAEs will be assigned to either DBPC Cycle and/or Dysport Cycle X based on the start date and time, or intensity increase date. For example, for presentation of TEAEs by Dysport Cycle, if the start time/intensity increase time of TEAE is at or after the time of treatment administration of Dysport Cycle X, Day 1 and prior to the time of treatment administration of Dysport Cycle X+1, Day 1, the TEAEs will be assigned to Dysport Cycle X.

In this study, an AESIs for Dysport is TEAEs that suggest a possible remote spread of effect of the toxin or events suggestive of hypersensitivity like reactions. TEAEs due to possible remote spread of the effects of Dysport will be identified using the list of MedDRA PTs compatible with the mechanism of action of BTX-A and based on the recommendations from

Statistical Analysis Plan

Version: Final v1.0
September-2018

Ipsen Protocol No. D-FR-52120-223
000000146513

Date of Issue: 21-

Covance Study ID:

the Committee for Medicinal Products for Human Use (CHMP) and the Food and Drug Administration (FDA). TEAEs potentially representing hypersensitivity reactions will be identified using the Standardised MedDRA Query (SMQ) (narrow search query) for hypersensitivity reactions. A list of MedDRA preferred terms, used to identify any potential AESI, is provided in Appendix IV.

All TEAEs identified using the search strategy described above will be medically evaluated during the study, before the database lock and unblinding, by the sponsor to identify events which could possibly represent ‘remote spread of effect of toxin’, or which are suggestive of ‘hypersensitivity reactions’ due to study treatment administration. Cases will be excluded if they are confounded by presence of alternative clinical etiologies (medical history, concomitant medication or diagnosis which could account for the symptoms); if they are considered to be local effects instead of distant spread as judged by the site of injection; the time period between the last study treatment administration and event onset is not in accordance with the expected mechanism of action; or due to insufficient information/evidence to make an assessment.

In the TFLs, only the final list of AESIs confirmed by the sponsor as “a possible remote spread event” or “hypersensitivity reactions” will be taken into account.

All AEs (with TEAEs flagged) reported during the study will be presented in a listing which will be sorted by treatment group in the respective assigned treatment cycle for that AE, subject ID, AE start date and time, primary system organ class (SOC), preferred term (PT), and verbatim text. The treatment cycle where the TEAE onset or intensity increased will be presented in the listing as well. Separate listings of all TEAEs, serious TEAEs, IMP-related TEAEs, TEAE of special interest, other protocol defined TEAEs, TEAEs leading to early withdrawal and TEAEs leading to death reported during the study will also be presented.

Overview tables will be produced for DBPC Cycle, Dysport Cycles and overall for the number and percentage of subjects with at least one of the following TEAEs, where subjects with more than one TEAE in a particular category are counted only once in that category. The number of TEAE occurrences will be provided as well. Note that for TEAEs that could only occur in the MS population (e.g. MS exacerbation), the denominator for the percentage calculation will relate to the number of MS patients; these TEAEs will be identified in the tables.

- any TEAE
 - intensity of TEAE (mild, moderate, severe)
 - Any IMP related TEAE
 - Any TEAE leading to withdrawal
- any serious TEAE
 - any IMP related serious TEAE
 - any serious TEAE leading to withdrawal
- any TEAE of special interest by type of AESI
 - any AESI leading to withdrawal
 - any serious AESI

Statistical Analysis Plan

Version: Final v1.0

September-2018

Ipsen Protocol No. D-FR-52120-223

000000146513

Date of Issue: 21-

Covance Study ID:

-
- any UTI TEAEs
 - UTI TEAEs leading to withdrawal
 - serious UTI TEAEs
 - TEAE leading to death

In view of the anticipated difference in duration of the Dysport and placebo treatment cycles, this overview table will also be provided including only TEAEs occurring up to 12 weeks after first IMP treatment administration.

A similar overview table will be produced for the number and percentage of subjects with at least one of the following events occurred pre-treatment for randomised subjects. The number of occurrences of the following events will be presented as well.

- any AE
 - Intensity of AE (mild, moderate, severe)
- any SAE
 - any SAEs leading to withdrawal
- AE leading to death

TEAEs will be summarised overall, for DPBC cycle, and Dysport Cycles with the number and percentage of subjects with TEAEs presented by primary SOC and PT. In addition, this table will be provided including only TEAEs occurring any time after first dose of IMP until up to 12 weeks after first IMP treatment administration. This will also be summarised by aetiology of NDO.

For AESIs, summary tables may also be produced following medical review of available information.

The same summaries for overall, for DBPC Cycle, and Dysport Cycles with the number and percentage of subjects with TEAEs presented by primary SOC and PT will be presented for serious TEAEs, IMP-related TEAEs, TEAEs leading to withdrawal, TEAEs of special interest, and other protocol defined TEAEs. TEAEs with PTs observed in $\geq 1\%$, $\geq 2\%$, and $\geq 5\%$ of subjects and IMP-related TEAEs with PTs observed in $\geq 1\%$, $\geq 2\%$, and $\geq 5\%$ of subjects will be summarised as well.

Additionally, TEAEs will be tabulated by decreasing overall PT frequency and intensity in each SOC and PT category.

The above will also be presented for SAEs.

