**PAGE 95/139** 

## 8.1.2.11 Adverse Events of Special Interest

The effects of Dysport® and all BTX products may spread from the area of injection to produce symptoms consistent with BTX effects. These symptoms have been reported hours to weeks after injection. Remote spread of toxin that affects swallowing and breathing can be life threatening, and there have been reports of death. The risk of symptoms is increased in subjects who have underlying conditions (e.g. disorders of the neuromuscular junction) that would predispose them to these symptoms.

Dysport® is contraindicated in individuals with known hypersensitivity to any BTX preparation or to any of the components in the formulation.

Adverse events of special interest (AESIs) for Dysport® are AEs that suggest a possible remote spread of effect of the toxin or hypersensitivity. A list of preferred terms of AESIs is provided in the Statistical Analysis Plan (SAP).

All AEs will be monitored by the sponsor to determine if they meet the criteria of AESIs. These AESIs will be further analysed to determine if there is a plausible possibility that they represent distant spread of toxin or hypersensitivity. In order to perform the analysis, variables including alternate aetiology (medical history, concomitant medication, or diagnosis which could account for the symptoms), location of Dysport® administration, and temporal relationship to Dysport® administration will be considered by the sponsor.

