1 SOURCE DOCUMENTS

This statistical analysis plan (SAP) Final v1.0 has been developed to supplement the statistical analysis described in the clinical trial protocol (D-FR-52120-223).

This SAP Final v1.0 describes the methodology and considerations of the planned analyses and a list of all the tables, figures and listings (TFLs) for this study. A detailed description of the planned TFLs will be provided in a separate TFLs shell document. Any minor changes to the TFL shells including but not limited to changes in TFL numbering, TFL footnotes or to the title of the TFLs will not require a revision to this SAP Final v1.0. Any major changes to the TFL shells or SAP Final v1.0 text may result in a revised amendment to this SAP.

This SAP and any amendments will be finalized prior to the lock of the clinical database. Any changes to the analyses described in this document or additional analyses performed to supplement the planned analyses will be described in the clinical study report (CSR).

The SAP was written based on the following documentation:

- International Council on Harmonisation (ICH) E9 guideline entitled, “Guidance for Industry: Statistical Principles for Clinical Trials” (ICH Guideline E9 1998)
- ICH E3 guideline entitled, “Guidance for Industry: Structure and Content of Clinical Study Reports” (ICH Guideline E3 1996)

Document	Date	Version
Protocol	14 September 2015	Final 1.0
Protocol Amendment 1	20 April 2018	Final 2.0
CCI [REDACTED]	19 September 2017	
eCRF	18 October 2017	Final 3.0
Data Model Specification for CRF Health	17 February 2016	Version 2
Trial Manager Tailoring Specification for CRF Health	23 May 2016	Version 4
I-QOL User Manual	March 2013	US English
Bladder Diary Terminology Document	07 April 2017	Version 3
EQ-5D-5L User Guide	April 2015	Version 2.1
222 SAP	08 March 2018	Final

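### SAP 7.7.1 counts potential AESIs that cannot be assessed as non-AESIs, so the AESI incidence shown within an arm can only fall or stay the same

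*SAP*

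**What the plan says.** SAP 7.7.1 defines AESIs in two steps.

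**Search.** Possible remote-spread events are found with a preferred-term list, and possible hypersensitivity events with a narrow standardised MedDRA query: "A list of MedDRA preferred terms, used to identify any potential AESI, is provided in Appendix IV".

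**Review.** The sponsor evaluates the hits during the study, before database lock and unblinding, "to identify events which could possibly represent" remote spread or suggest hypersensitivity. A hit is removed on any of four grounds: an alternative clinical cause, a local effect, implausible timing, "or due to insufficient information/evidence to make an assessment".

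The section then restricts what is shown: "In the TFLs, only the final list of AESIs confirmed by the sponsor as" possible remote spread or hypersensitivity is used. The overview table has rows for "any TEAE of special interest by type of AESI". System organ class and preferred term (SOC/PT) tables are planned for "TEAEs of special interest, and other protocol defined TEAEs". Further AESI summary tables after medical review are left optional, with no content given.

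Protocol 8.1.2.11 sets the review standard: "These AESIs will be further analysed to determine if there is a plausible possibility that they represent distant spread of toxin or hypersensitivity". It names alternate aetiology, injection location and timing as variables to consider, in a list that is open. Protocol 9.4.7 requires AESI incidence by treatment group.

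**The concern.** The first three grounds each give a reason to think that the event is not an AESI. The fourth gives none. It records that the question could not be answered, yet the event ends up where the rejected events do.

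Remote spread is a main named risk of the product, and protocol 8.1.2.11 describes it as potentially life-threatening. Protocol 1.5 chose two doses so that they could be separated on the balance of efficacy and safety. A by-arm AESI count that silently treats unknown as no is less informative for that purpose than one that shows the unknowns.

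**Working it through.** The plan gives no figure to reproduce here, so the check is mainly a comparison of texts, with a little arithmetic for scale.

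**1. Effect of the rule within an arm.** Let C be the subjects with a confirmed AESI, U the subjects whose only search-positive events were removed for lack of information, and N the subjects in the arm.
- Incidence shown: C/N.
- Incidence if every unassessable case were in truth an AESI: (C + U)/N.
- Difference: U/N, which is never negative. So the rule lowers the within-arm incidence or leaves it unchanged.

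**2. Scale.** Planned arms in the DBPC cycle have 110 subjects each: 110 on 600 U, 110 on 800 U, and 55 + 55 = 110 on pooled placebo (protocol 3.3.1; SAP 2.2). The documents give no value for U, so these values are assumed:

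| U (assumed) | U/110 |
|---|---|
| 0 | 0.00 points |
| 1 | 0.91 points |
| 2 | 1.82 points |
| 3 | 2.73 points |

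In Dysport Cycle 1, if every placebo subject were retreated, each dose would have 110 + 55 = 165 subjects, and one subject would be 1/165 = 0.61 points.

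**3. Effect on the Dysport-placebo difference.** With 110 per arm, the difference changes by (U in placebo − U in Dysport)/110. One case in the Dysport arm alone lowers it by 0.91 points, one in placebo alone raises it by 0.91, and one in each leaves it unchanged. Review comes before unblinding, so nothing in the documents fixes the sign.

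**4. Fit with the documents' own standards.**
- SAP 7.7.1 and protocol 8.1.2.11 both ask about possibility. A case with too little information has not been shown to be implausible.
- SAP 6.2.1.2 keeps missing AE intensity or causality as its own category. SAP 6.2.2 counts an AE with a missing onset date as treatment-emergent unless a partial onset date or the stop date shows otherwise. In both places missing information stays visible or is resolved towards inclusion. The AESI rule resolves it towards removal.

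**The case against.** The other side has real points.

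- **The events are not lost.** They remain in the all-TEAE SOC/PT tables, in the IMP-related tables where judged related, and in the listings with treatment group, cycle and verbatim term. This stands and limits the consequence. It does not give a count of subjects: preferred-term rows cannot be summed when one subject may have several, and those outputs, as described, do not give the ground for removal.
- **Cases may be few.** Protocol 8.1.3 asks investigators to obtain enough information to judge causality. This stands, though reporting few cases also costs little.
- **A strict definition is legitimate.** The protocol can be read as requiring a positive finding of plausibility, which thin evidence cannot support. This is a fair reading, and it is why the confirmed set should stay as it is. It does not require that unassessable events be shown as non-AESIs.
- **Safety analysis is descriptive** (protocol synopsis, Safety endpoints). No test or decision rule changes.

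A reader might infer that the plan has no table of search hits or of exclusions by ground. The documents do not support that. SAP section 1 refers to a list of outputs and says "A detailed description of the planned TFLs will be provided in a separate TFLs shell document"; the shells and Appendix IV are not available here, and SAP 7.7.1 leaves room for extra AESI tables. A reader might also infer that the SAP contradicts the protocol. Because the protocol's list of variables is open, what can be shown is a poor fit in wording, not a change to the protocol.

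**Conclusion.** The point holds as a matter of reporting. Unassessable potential AESIs are counted as non-AESIs by a stated rule, and within an arm that rule can only lower AESI incidence or leave it unchanged. The size is unknown; one subject is 0.91 points in a 110-subject arm, assuming planned enrolment.

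Two stronger readings should be resisted. The first is that the rule favours Dysport over placebo: blinded review leaves the direction of any effect on the difference open. The second is a projected AESI rate from protocol 1.3.2, where muscular weakness occurred in 14/427 = 3.3% of patients, or 110 × 14/427 = 3.6 expected subjects per arm. That projection would need the rate to carry over to 600 U and 800 U, the term to be in Appendix IV, and every assessable hit to be confirmed. The last is doubtful, because the other three grounds also remove cases and all subjects have SCI or MS, which could supply an alternative explanation for weakness.

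This is a low-priority, cheap improvement.

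**What to change.** In SAP 7.7.1:

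1. Keep the confirmed-AESI set and its tables unchanged.
2. Take insufficient information out of the grounds for exclusion. Classify those events as not assessable / cannot be excluded.
3. Beside the confirmed AESIs, report the number and percentage of subjects with such events by treatment group, for the DBPC cycle and the Dysport cycles. Add a row for subjects with a confirmed or a not-assessable event, because a subject may have both.
4. The same table can show subjects with any search-positive event and exclusions by each remaining ground. If the unseen shells already contain this, a cross-reference in 7.7.1 is enough.

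The cost is one category and one table. No new data are needed, assuming the blinded review records the ground for each removal. The downside is that the added category is less specific than the confirmed set, so it must be read beside that set and not in place of it.

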The retreatment criteria are as follows:

- 1) Retreatment requested by subject;
- 2) More than 12 weeks (84 days) since the previous IMP administration;
- 3) CCI [REDACTED]
[REDACTED]
[REDACTED]
[REDACTED];
- 5) In the investigator's opinion it is safe and appropriate to provide retreatment.

A patient may only be retreated if eligible based on the study retreatment criteria. The bladder diary device/portal may provide an indication that the patient is within 30% of their Baseline (Screening) UI level, however to confirm eligibility a manual calculation can be performed by multiplying the weekly number of UI episodes on the screening bladder diary by 0.7. If the subject has a current number of weekly UI episodes greater than this calculated number then the subject is within 30% of their Baseline UI level and meets the retreatment criterion #3.

Example calculation:

- Study Baseline (Screening) number of weekly UI episodes = 28 episodes
 $28 \text{ episodes} \times 0.7 = 19.6$ (rounded up to 20)
- Subject is therefore eligible for retreatment if current weekly UI episodes are 20 or more.

Retreatment should ideally occur within 14 days of confirmation of eligibility for retreatment and can occur up to and including Week 104 following the first IMP administration of the first period.

Retreatment follow-up

Follow-up after each retreatment follows the same schedule as the first IMP administration (Treatment 1).

- Week 1 (Day 8) (telephone)
- Week 2 (Day 15) (clinic visit)
- Week 4 (Day 29) (telephone)
- Week 6 (Day 43) (clinic visit)
- Week 12 (Day 85) (clinic visit; the retreatment could be requested by subject from this visit)
- Every 12 weeks (telephone visits; until retreatment received or EOS at Weeks 104 to 116).

Details of the procedures performed at each Retreatment Follow-up Visit in the Dysport cycle are contained in [Appendix V](#).

End of Study Visit

The EOS Visit will take place between 104 and 116 weeks after the first IMP administration on Day 1. Subjects may receive study retreatment up to and including Week 104 and a minimum of 12 weeks of follow-up is required after each IMP administration. For those subjects completing the study, the EOS Visit will occur:

- At Week 104 after the first IMP administration, if it has been more than 12 weeks since the previous IMP administration.

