7 STATISTICAL METHODS

7.1 General Principles

All data processing, summarisation and analyses will be performed using the SAS Environment / Version 9.4 (or later) of the SAS[®] statistical software package.

All data collected during the study will be presented in listings without any imputation by treatment group, subject, assessment and visit (where applicable), unless otherwise specified.

Data will be presented in summary tables by treatment group (as described below), assessment and visit (where applicable).

Overall, the analysis strategy is to evaluate efficacy and safety data from the initial DBPC Cycle and to evaluate efficacy and safety over repeated Dysport treatments, using analyses by Dysport Cycle (Dysport Cycle 1, 2...etc.), as illustrated in schematic diagram later in this section. In general, tables associated with the DBPC Cycle will be separate from the tables assessing repeat treatment with Dysport which are presented by Dysport Cycle:

- During analysis of the DBPC (DBPC cycle), data will be displayed using the following treatment group labels, in the order presented:
 - Placebo
 - Dysport 600 U
 - Dysport 800 U
 - All Dysport
- During analysis by Dysport Cycle, data will be displayed by number of Dysport treatments (see diagram below) using the following treatment group labels:
 - Dysport Cycle 1
 - Dysport 600U
 - Dysport 800U
 - All Dysport
 - Dysport Cycle 2
 - Dysport 600U
 - Dysport 800U
 - All Dysport
 - Dysport Cycle X

Statistical Analysis Plan

Version: Final v1.0
September-2018
Ipsen Protocol No. D-FR-52120-223
000000146513

[figure not shown]
Date of Issue: 21-
Covance Study ID:

- Dysport 600U
- Dysport 800U
- All Dysport

Analysis of Dysport Cycle 1 will therefore include (see diagram below):

- Data from subjects who received a Dysport treatment after having initially received placebo as their first study treatment on Day 1 i.e. will only use data from their first Dysport treatment,
- Data from subjects who received Dysport as their first study treatment on Day 1

Schematic diagram summarising concept of Dysport Cycles:

Descriptive summary statistics for continuous variables will include the number of subjects (n), mean, standard deviation (SD), median, minimum and maximum.

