Descriptive summary statistics for categorical variables will include frequency counts and percentages [n (%)]. The denominator for percentage calculations will be the number of subjects in the analysis population for the designated treatment cycles. Unless stated otherwise in the table shells (e.g. for the TEAE of MS relapse, the denominator only relates to the number of MS subjects),

Dates will be displayed as DDMMMYYYY.

Overall, in the statistical tables the category “Missing” will be presented if the number missing is > zero for at least one treatment group.

Unless otherwise specified, the eCRF recorded strata (i.e. the correct strata) will be analysed for all used in all the data displays.

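### Adverse events are counted over whole Dysport Cycles of unequal length, and the 12-week window is used only after the first injection, so incidence can look lower in later cycles because they are observed for less time

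*SAP*

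**What the plan says.** SAP 7.1 sets the purpose of the by-cycle tables: "to evaluate efficacy and safety over repeated Dysport treatments, using analyses by Dysport Cycle". SAP 7.7.1 then fixes how events are counted.

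- **Window.** An event starting after the injection of Cycle X and "prior to the time of treatment administration of Dysport Cycle X+1, Day 1, the TEAEs will be assigned to Dysport Cycle X". No upper limit is stated, so a subject's last cycle runs to the last visit.
- **Measure.** In the overview, "subjects with more than one TEAE in a particular category are counted only once in that category". For the SOC/PT tables, "TEAEs will be summarised overall, for DPBC cycle, and Dysport Cycles with the number and percentage of subjects".
- **Denominator.** SAP 7.1: "The denominator for percentage calculations will be the number of subjects in the analysis population for the designated treatment cycles". It is subjects, not time at risk.
- **Fixed window.** For the overview, "this overview table will also be provided including only TEAEs occurring up to 12 weeks after first IMP treatment administration". The SOC/PT table has a 12-week version tied to the same first administration. The SAP's stated reason is that Dysport and placebo cycles are expected to differ in length.
- **Follow-up.** SAP 2.2: "a minimum of 12 weeks of follow-up is required after each IMP administration".

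The visible text specifies no exposure-adjusted rate and no time-to-first-event analysis for safety. SAP 7.5 gives exposure in weeks for the study as a whole; its Dysport Cycle part gives only numbers of treatments.

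**The concern.** The SAP's reason for the 12-week tables applies equally between one Dysport Cycle and the next. Retreatment is on request, after more than 12 weeks and up to Week 104. A subject who responds for a long time therefore has one long cycle, while a cycle begun near Week 104 has about 12 weeks. The percentage of subjects with at least one event rises with observation time whenever the event has a background hazard. Protocol 1.7 says that UTI does: it separates a background incidence from the incidence due to the procedure.

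Safety of the two doses is a study objective. If whole-cycle percentages decline from Cycle 1 to Cycle 4, a reader of the study report could take this as improving tolerability with repeated treatment, when the tables alone cannot tell that from shorter follow-up.

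There is also a gap in the first Dysport exposure. Dysport Cycle 1 includes the first Dysport treatment of subjects who began on placebo, but for them the first-administration window is a placebo window. By plan this is 55 of up to 110 + 55 = 165 subjects per dose, or one third if all are retreated.

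**Working it through.** **Range of cycle length.** Protocol 3.4 gives a maximum participation of 116 weeks, which reproduces as 104 + 12. The shortest completed cycle is just over 12 weeks. The longest is about 104 weeks, for a subject given Dysport on Day 1 and never retreated.

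**Effect of length alone.** The documents give no event rate. Assume a constant hazard with 15% of subjects having a UTI per 12 weeks (range 10 to 20%). Then P(at least one event in L weeks) = 1 − (1 − p)^(L/12).

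| L (weeks) | p = 10% | p = 15% | p = 20% |
|---|---|---|---|
| 12 | 10.0% | 15.0% | 20.0% |
| 36 | 27.1% | 38.6% | 48.8% |

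For example, 1 − 0.85^3 = 0.386.

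**Effect under the study's timetable.** The documents give no retreatment interval either, so these are assumed. Simulated intervals are lognormal with a floor of 13 weeks. Retreatment is possible up to Week 104, and follow-up ends at the later of Week 104 and 12 weeks after the last injection. The hazard is the same in every cycle (15% per 12 weeks).

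| Assumed interval | Cycle 1 | Cycle 2 | Cycle 3 | Cycle 4 |
|---|---|---|---|---|
| Median 36 weeks, log-SD 0.6 | 41% | 38% | 30% | 23% |
| Same, placebo-first subjects included (16-week placebo cycle) | 41% | 37% | 29% | 22% |
| Median 24 weeks, log-SD 0.3 | 28% | 28% | 28% | 25% |
| Events only around the procedure | 15% | 15% | 15% | 15% |

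**Other hazard assumptions.** These use exponential intervals with a 36-week median.

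- At a constant 0.5 UTI per year, mean cycle length is 43, 36, 27 and 19 weeks, and the percentage reads 32.3, 28.0, 21.9 and 16.6%.
- With a cumulative hazard of 0.2 in the first 2 weeks plus 0.2 per year afterwards, it reads 30.4, 28.5, 26.0 and 23.9%.

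**With a 12-week window after each administration.** When follow-up is complete, the percentage is flat: 10.9% in every cycle at 0.5 per year, and 21.8% with the early peak. The window always fits, because retreatment requires more than 84 days.

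**When a real change is present.** If the hazard rose by 20% per cycle, the whole-cycle percentages (36-week median, log-SD 0.6) would read about 41/43/40/36%. The 12-week window would give 1 − 0.85^1 = 15.0%, 1 − 0.85^1.2 = 17.7%, 1 − 0.85^1.44 = 20.9% and 1 − 0.85^1.728 = 24.5%.

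**Incomplete windows.** SAP 7.8 also produces all tables at a data cut-off. With entry assumed to be staggered so that subjects have 12 to 104 weeks of follow-up, about 20, 33 and 51% of Cycles 2 to 4 would have under 12 weeks. At 0.5 per year, a naive 12-week percentage would then itself fall from 10.7% in Cycle 1 to 8.0% in Cycle 4.

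**The case against.** **Safety is descriptive.** The protocol plans no inferential safety comparison, and the SAP specifies no test or trend across cycles. "The number of TEAE occurrences will be provided as well", events are listed with start dates and cycle, and SAP 7.6.6.4 summarises time between treatments by cycle. This stands as a limit on severity. It does not remove the point, because none of these outputs gives an incidence over equal time, and SAP 7.1 says repeat-treatment safety is evaluated by cycle.

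**Some events are barely affected.** Protocol 8.1.2.11 describes spread of toxin effect as appearing hours to weeks after injection, and the sponsor's review excludes events whose timing does not fit the mechanism. Toxin-spread events should therefore depend little on cycle length. This stands; the concern is mainly with events that have a background rate, UTI above all.

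**Doses.** A reader might infer that a longer-acting dose will look less safe because its cycles are longer. The documents do not support this as a general statement. No difference in cycle length between 600 U and 800 U is given, and the first-administration tables already compare the randomised groups over equal windows in the placebo-controlled cycle. Only whole-cycle comparisons in the repeat cycles would be exposed, and only if cycle lengths did differ.

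**Unseen tables.** The table shells are a separate document and the appendix entries are redacted, so per-cycle 12-week tables may exist there. The text of 7.7.1 names only the first administration.

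**Conclusion.** The point holds as a matter of comparability: whole-cycle percentages rest on unequal observation time, and the SAP's own remedy stops at the first administration. Incidence of events with a background hazard can therefore appear lower in later cycles. Under the assumptions tried, the artefact ranges from close to a halving over four cycles (41% to 23%), through a small drop confined to Cycle 4 (28% to 25%), to none.

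A reader might infer that incidence will fall with every cycle for no biological reason. That goes too far. The direction and size depend on UTI rates, hazard shape and retreatment intervals that the documents do not give; the first two or three cycles can be level. A real change in risk, or selection of the subjects who reach later cycles, could add to the artefact or offset it. The change is worth making because it is cheap; no planned test depends on it.

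**What to change.** In SAP 7.7.1:

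- For each Dysport Cycle, also produce the overview (including UTI, adverse events of special interest and serious TEAEs) and the SOC/PT table, counting events from that cycle's administration to 12 weeks after it. This covers the first Dysport treatment of placebo-first subjects.
- Report exposure weeks per cycle beside these tables.
- Where windows are incomplete, at the data cut-off or after early discontinuation, use a 12-week time-to-first-event (cumulative incidence) estimate, or state how many subjects completed the window.
- Keep the whole-cycle tables for late events, and add a note that a fixed window does not remove selection into later cycles.

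Events per patient-year could be added but should not replace the window. With the early-peak assumption and a 36-week median, they rise from 44 to 74 per 100 patient-years over Cycles 1 to 4 with no change in risk.

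The cost is SAP wording and a few repeated tables from dates already collected, and SAP 1 allows amendment before database lock. The downside is that late-onset events appear only in the whole-cycle tables.
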